6.4 Treatments

Non-interventional study – no treatments/pharmacotherapy are pre-defined in the protocol.

All clinical decisions will be fully responsibility of the investigator.

7 Conduct

7.1 Data collection overview

Table 1. Study Flow Chart

Study variables	Day 1	Prospective period* (approx. 12 months)			
		Collection data points			
Timing of data collection	Day 1 visit	3-months (90 days \pm 14 days)	6-months (180 days \pm 14 days)	9-months (270 days \pm 14 days)	. End of fw-up (12 months) (365 days \pm 14 days)
Informed consent	X				
Inclusion criteria	X				
Exclusion criteria	X				
Anthropometric Information (Weight, Height, BMI)	X				
IBD type (CD or UC)	X				
Socio-demographic variables	X				
Smoking habits	X				
Family history of IBD	X				
Medical history / Comorbidities	X				
Date of diagnosis of CD or UC	X				
Date of diagnosis of moderate to severe CD or UC	X				
Clinical Characterization of Disease – (location, behavior, EIM)	X				
Steroid behavior	X				
Disease activity: CD (HBI score or CDAI); UC (partial/total Mayo Score)	X				X
Eligibility for 12-month follow up	X				
SF-36	X				
EQ-5D	X				
IBDQ**	X				
WPAI	X				
Previous treatments or regimens ^{1,2}	X				
Treatment started at Day 1	X				
Treatment at follow-up		X	X	X	X
Previous surgeries for IBD	X ²				
Hospitalizations	X ²				
Consumption of health resources related with IBD management	X ²				
Previous imaging and laboratory testing form	X ²				

¹ Excludes new treatments prescribed at Day 1 visit. ² Retrospective data collection (approx. 3 years)

* Prospective follow-up only for patients with active IBD at Day 1. In this period, data collection is expected to occur quarterly for all registered medical appointments.

** Not applicable for patients who have a colostomy or ileostomy.

7.2 Study Variables

Data will be collected from medical charts and during the routine clinical appointment, for the following variables:

Socio-Demographic variables

- Date of birth;
- Gender;
- Professional status (employed, unemployed, retired, student, other).

Clinical variables

- IBD type: CD or UC;
- Date of diagnosis of CD or UC;
- Date of diagnosis of moderate to severe CD or UC (if not the same as previous);
- Family history of IBD;
- Smoking habits;
- Medical History / Comorbidities;
- Disease presentation [location, behavior, extraintestinal manifestations (EIM)];
- Steroid behavior (dependent or refractory);
- Colonoscopy in the previous year suggestive of inadequate control of activity (yes/no) (qualitative data/Mayo subscore);
- Calprotectin levels in the previous year suggestive of inadequate control of activity (i.e., calprotectin >200ug/g) (yes/no) (qualitative data);
- Eligibility for 12-month prospective follow up (yes/no).

Disease activity (at Day 1 and 12 months follow up appointment)

- For CD patients: Harvey Bradshaw Index (HBI) score or Crohn's Disease Activity Index (CDAI);
- For UC patients: 9-item partial Mayo Score (always collected) and the total Mayo score (when available).

The Harvey Bradshaw Index (HBI) score considers five easily assessed dimensions (general well-being, abdominal pain, number of liquid stools per day, abdominal mass, and complications). These dimensions are scored from the previous day (no diary cards are required). Patients with $HBI \geq 8$ are classified as presenting moderate to severe active disease (29).

The Crohn's Disease Activity Index (CDAI) evaluates the severity of signs and symptoms of CD. Collected data include information on the number of liquid stools, intensity of abdominal pain, general well-being, presence of comorbid conditions, use of medications for diarrhea, physical examination, and laboratory findings (abdominal mass, hematocrit, body weight), yielding 8 items that are combined with data from a 7-day diary to obtain the total CDAI score. Higher scores indicate a greater disease severity. Moderate to severe active CD is defined as $CDAI \geq 220$ (30).

The Mayo score is composed of four categories (bleeding, stool frequency, physician assessment, and endoscopic appearance) rated from 0–3 that are summed to give a total score that ranges from 0–12. The partial Mayo Score (pMayo) was previously compared with the full Mayo score and categorizes patients as being in remission (score of 0–2), having mild disease (pMayo of 3 or 4) or moderate to severe disease (pMayo of ≥ 5) (31).

Health-Related Quality of Life and Work Productivity (at Day 1)

- 36-item Short Form Health Survey (SF-36)
- 5-dimensional EuroQoL measure (EQ-5D)
- Inflammatory Bowel Disease Questionnaire (IBDQ) - 32 items
- Work Productivity and Activity Impairment Questionnaire (WPAI) – 6 items

The Short Form-36 (SF-36) evaluates 8 health dimensions: physical functioning, bodily pain, role physical (limitations due to physical problems), role emotional (limitations due to personal or emotional problems), mental health, social functioning, vitality, and general health perceptions. Based on these 8 scales, two weighted scores are generated: the physical component summary (PCS) and the mental component summary (MCS) score. Scores range between 0 and 100, with higher scores indicating a better quality of life (32).

For more information, please consult

http://www.rand.org/health/surveys_tools/mos/mos_core_36item_survey_print.html.

EuroQoL questionnaire (EQ-5D-5L) considers five attributes of quality of life evaluation, i.e mobility, self-care, usual activity, pain/discomfort, and anxiety/depression. Each dimension has five possible levels, 1-no problems, 2 slight problems, 3-moderate problems, 4-severe problems, 5-extreme problems, thus defining a total of 3125 possible health states, each one referred to in terms of a 5 digit code. EQ-5D also include an additional visual analogic scale (EQ-VAS), which ranges from 0, worst imaginable health state, to 100, best imaginable health state (33). For more information, please consult <http://www.euroqol.org/>.

The Inflammatory Bowel Disease Questionnaire (IBDQ) is a 32-item questionnaire that measures 4 dimensions: bowel function, emotional status, systemic symptoms, and social function. Within dimensions, each question presents seven possible answers/points. The score for each dimension results from the sum of points. Hence, the total score ranges from 32 to 224, with higher scores representing better quality of life (34). A Portuguese (Brazil) version was already validated (35). The IBDQ is not validated for patients with ostomies and therefore should not be applied for these patients. For more information, please consult <http://www.flintbox.com/public/project/641>.

The Work Productivity and Activity Impairment questionnaire (WPAI) assesses the impact of IBD on work productivity and daily activities during the previous 7 days. In brief, the WPAI questions are: 1) if currently employed, 2) hours missed due to disease, 3) hours missed other reasons, 4) hours actually worked, 5) degree disease affected productivity while working, 6) degree disease affected regular activities (7). WPAI generates four component scores: percentage of work time missed (absenteeism); percentage of impairment while working (presenteeism); percentage of overall work impairment (absenteeism and presenteeism combined); and percentage of activity impairment. Unemployed patients only answer to questions related to employment status and activity impairment. Scores for WPAI range from 0% ('no impairment') to 100% ('total loss of work productivity/activity'). For more information, please consult http://www.reillyassociates.net/WPAI_General.html.

Treatment

- Previous treatments or regimens (aminosalicylates, steroids, immunomodulators, immunosuppressors, biologics, probiotics, antibiotics); start date; end date, dose, reason for discontinuation;
- Treatment started at Day 1 (name, dose);
- Previous surgeries for IBD.

At follow up appointment only:

- Therapeutic strategy: maintain current treatment vs discontinued;
- If discontinued, new treatment (name, dose, start date), and reason for discontinuation.

Other health care resources related with IBD management

- Imaging and laboratory testing;
- Surgeries;
- Hospitalizations;
- Consultations;
- Adverse Events.

8 Management and Reporting of Adverse Events

8.1 Definitions

Adverse Events

An adverse event (AE) is any untoward medical occurrence in a subject administered a medicinal product and which does not necessarily have to have a causal relationship with this treatment. An AE can therefore be any unfavourable and unintended sign (including an abnormal laboratory finding), symptom, a new disease or worsening in severity or frequency of a concomitant disease, temporally associated with the use of a medicinal product, whether or not the event is considered causally related to the use of the product.

Adverse Reactions

An adverse reaction is an AE for which there is at least a reasonable suspicion of a causal relationship between an AE and a suspected medicinal product.

Causality

The following definitions of **Related** should be used to characterize the suspected causality of an AE. This assessment should be based on the Investigator's consideration of all available information about the event, including temporal relationship to drug administration, recognized association with drug product/class, pharmacological plausibility, and alternative etiology (e.g., underlying illness, concurrent conditions, concomitant treatments):

Related: There is a reasonable possibility that the drug caused the event. There is a reasonable temporal relationship between the drug administration and the event, and no other obvious alternative explanation for the occurrence of the event.

Not related: There is not a reasonable possibility that the drug caused the event. There is evidence for (an) alternative explanation(s) for the event (eg, the event is explained by one or more of the following: a) the subject's medical condition (medical history, disease progress, indication), b) a concomitant medication for which the event is labelled, or c) AE occurrence prior to the introduction of the medicinal product.

The investigator must make an assessment of causality using the above definition. Causality cannot be assumed in the absence of the investigator's assessment.

8.2 Collection and Recording of Adverse Events

Collection and recording of AEs will commence after the study participant has provided informed consent.

If during the conduct of the study a member of the research team is spontaneously informed of an AE, ADR, SSR, beneficial event or product quality issue, where the event/issue pertains to a Takeda/ Multilab product (or unbranded generic which active principle is also manufactured by Multilab), such information should be reported to the Sponsor within 24 hours of Investigator's team awareness, including the Investigator itself. The investigator should assess the causality for the adverse events and the causality should not be assumed if there is no investigator's assessment.

Follow-up information

After notification of the initial AE Report form, the Investigator may be contacted by the Sponsor to obtain additional information on the event or for data clarification. The investigator shall make best effort to obtain the requested additional information. All new additional information obtained on the event should be recorded on an AE Report form and notified to the Sponsor within 24 hours of Investigator awareness of the new information.

8.3 Reporting of Adverse Reactions

The Sponsor is responsible for submission of adverse reactions to regulatory authorities in accordance with local reporting requirements or the Sponsor's post marketing commitments, with the exception of Individual Case Safety Reports s not collected as part of the study and reported spontaneously by investigator or study participant to national competent authorities as in 12.2 above.

8.4 Other Safety Information

If the investigator becomes aware of any of the following events associated with a Takeda product during the study, whether or not associated with an AE, the event should be recorded on an AE Report form /Pregnancy Report form and submitted to the Sponsor within 24 hours of investigator awareness.

- **Use during pregnancy**
- **Overdose:** This refers to the administration of a quantity of a drug given per administration or cumulatively, which is above the maximum recommended dose according to the authorised product information. Clinical judgement should always be applied.
- **Off-label use:** This relates to situations where the drug is intentionally used for a medical purpose not in accordance with the authorised product information.
- **Misuse:** This refers to situations where the drug is intentionally and inappropriately used not in accordance with the authorised product information.
- **Abuse:** This corresponds to the persistent or sporadic, intentional excessive use of a drug, which is accompanied by harmful physical or psychological effects.

- **Medication error:** This refers to any unintentional error in the prescribing, dispensing, or administration of a drug while in the control of the healthcare professional or patient.
- **Accidental occupational exposure:** This refers to exposure to a drug, as a result of one's professional or non-professional occupation.

9 Data Quality Control and Assurance

9.1 Quality Control

The study will use electronic data collection, for which a set of automatic data checks with data queries will be programmed for data cleaning. Manual data monitoring will include on and off site visits and on site Source Data Verification (SDV) will include the check of the Signed Informed Consent for all subjects. Source documents (e.g., medical records, original laboratory records) and Signed Informed Consent should be available to study monitors whenever possible, and consent to such access will be explicitly included in the Informed Consent Form.

Additional details will be specified in the Monitoring Plan.

9.2 Audit from Quality Assurance Unit

The Quality Assurance (QA) unit may audit the study to ensure that study procedures comply with the protocol and standard operating procedures, and that collected data is correct and complete.

9.3 Inspection by IEC or Competent Authority

Representatives from IEC or Competent Authority may in rare cases wish to inspect the study on site. Upon receiving notification of such inspection, the Study Site Responsible must immediately contact Global Research and must make the records available as requested.

9.4 Data Management

Data management will be performed by the designated CRO, **CCI** Data Management will be carried out according to a Data Management Plan, which must be written and

approved before the design of the study database is finalized. The data management provider should approve all data formats before the data collection tools are made available to the sites.

If the written informed consent of a subject is known not to be available in spite of it being required, data for this subject is not entered into or is deleted from the database.

If a subject is erroneously included in the study more than once only the data relating to the first inclusion will be kept in the database and be available for analysis. Data from later inclusions will be transferred to the first dataset when relevant, i.e., if collected within the time frame of the first follow-up period.

The current Standard Coding Instructions for coding of medical history, concomitant illness **CCI** and concomitant medication **PPD** must be followed.

The subjects will be identified in the database only by Study ID, Site ID, and subject number.

9.4.1 Data Collection Tools and Flow

The Study Site will receive data collection tools (access to eCRFs and PRO tools) from Takeda or Designee. Whenever possible, complete data sets should be entered. Text field entries and any data collected on paper should be legible and follow the requested language standard.

The Study Site Responsible must sign off the complete data set for each subject, confirming the collected data. ADR data reported according to section 8 and data on serious AE/ADR reactions collected according to section 7 should be signed off separately by a physician who may or may not be involved in the study.

Data collection will be implemented by means of a study-specific eCRF. A detailed Data Validation Plan that will identify missing data, out-of-range data, and other data inconsistencies will be implemented prior to study start. To resolve any questions arising from the data review process, data queries and/or site notifications will be created in the EDC system database for site resolution and closed by the sponsor reviewer.

CC1 will also be responsible for study's follow up, including regular contacts with investigators and in-house monitoring (review of data collected and support on queries resolution). At any time during the course of the study, the investigator (or site staff) may contact the study monitor in order to clarify any study procedures. All source documentation supporting entries into the eCRF must be maintained and readily available.

10 Statistical Methods and Determination of Sample Size

Statistical analyses will be performed by the designated CRO, CC1 This section describes the statistical analyses as foreseen at the time of planning the study. Any known deviations from the planned analyses, the reason for such deviations and all alternative / additional statistical analyses that may be performed as well as the final statistical analysis must be described in a revised Statistical Analysis Plan (SAP) before completion of data collection. All later deviations and / or alterations will be summarised in the Clinical Study Report.

10.1 Statistical Analysis Plan

This study is observational and epidemiological methods will be employed for data analyses. Data analysis will be performed using SAS ® (version 9.4; SAS Institute Inc, Cary, USA - running under Windows 8).

Descriptive analysis will be performed of all collected data except data collected only for the purpose of data cleaning, i.e, all data listed in section 7.

10.1.1 Study Endpoints

The main study endpoints are:

Primary Endpoints:

- For Crohn's Disease: Proportion of patients with active disease (HBI ≥ 8 or CDAI ≥ 220 points - based on criteria used by the site) at Day 1.
- For Ulcerative Colitis: Proportion of patients with active disease (9-point partial Mayo score ≥ 5) at Day 1.

Secondary Endpoints:

- Distribution of age, gender, smoking habits, professional status by IBD type.
- Distribution of clinical variables by IBD type.

- Therapies for IBD (aminosalicylates, steroids, immunomodulators, immunosuppressors, biologics, antibiotics, probiotics, surgeries) within the previous 3 years.
- Proportion of biologic-experienced patients.
- Proportion of patients who have not responded previously to biologic therapies and reason.
- IBD treatment introduced at Day 1.
- Socio-demographic, clinical and treatment-related variables in patients with moderate to severe activity of CD (HBI \geq 8 or CDAI \geq 220 points) versus patients with light or no activity (HBI $<$ 8 or CDAI $<$ 220 points).
- Socio-demographic, clinical and treatment-related variables in patients with moderate to severe activity of UC (partial Mayo score \geq 5) versus patients with light or no activity (partial Mayo $<$ 5).
- Among patients who had moderately to severely active CD at Day 1: HBI or CDAI score after 12 months.
- Among patients who had moderately to severely active UC at Day 1: Partial Mayo score after 12 months.
- Among patients who had moderately to severely active CD or UC at Day 1: Treatment after 12 months; in case of change of current treatment: reason for change
- Mean score of EQ-5D by IBD type.
- Mean score of different components of SF-36 by IBD type.
- Mean total score of IBDQ and by domain (bowel symptoms, systemic symptoms, emotional function and social function). The IBDQ is not validated for patients with ostomies and therefore should not be applied for these patients.
- Mean of subjects total percentage of work impairment (WPAI).
- Mean work time missed (WPAI).
- Mean impairment while working (WPAI).
- Mean total activity impairment (WPAI).
- Health resources (previous 3 years) imaging and laboratory testing, surgeries, hospitalizations, consultations and adverse events.

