informed consent. Patients will be excluded if (1) presenting indeterminate or not classified colitis, or (2) having current or previous participation in interventional clinical trials (within the last 3 years), or (3) presenting mental incapacity, unwillingness or language barriers precluding adequate understanding or cooperation, or (4) hospitalized patients at Day 1, or (5) in current off label treatment with Vedolizumab.

Duration of data collection per subject

Cross-sectional at Day 1, with retrospective data collection over the previous 3 years. For patients enrolled in the prospective phase, information will be collected at all clinical appointments occurring within 12 months.

Criteria for evaluation

Population descriptors

Date of birth, gender, smoking habits, professional status (employed, unemployed, retired, student, other), date of diagnosis of CD or UC, date of diagnosis of moderate to severe CD or UC (if not the same as previous), family history of IBD, disease presentation (location, behavior, extraintestinal manifestations), steroid behavior, comorbidities.

Main outcome variables

Primary Endpoints:

- For Crohn's Disease: Proportion of patients with active disease (HBI ≥ 8 or CDAI ≥ 220 points - based on criteria used by the site) at Day 1.
- For Ulcerative Colitis: Proportion of patients with active disease (9-point partial Mayo ≥ 5) at Day 1.

Secondary Endpoints:

- Distribution of age, gender, smoking habits, professional status, family history, educational level, subject income by IBD type.
- Distribution of clinical variables (e.g.: type of IBD, steroid behavior, anthropometric information, medical history and comorbidities, clinical characterization of disease) by IBD type.
- Therapies for IBD (aminosalicylates, steroids, immunomodulators, immunosuppressors biologics, antibiotics, probiotics, surgeries) within the previous 3 years.
- Proportion of biologic-experienced patients.

- Proportion of patients who have not responded previously to biologic therapies and reason.
- IBD treatment introduced at Day 1.
- Socio-demographic, clinical and treatment-related variables in patients with moderate to severe activity of CD (HBI \geq 8 or CDAI \geq 220 points) versus patients with mild or no activity (HBI < 8 or CDAI < 220 points).
- Socio-demographic, clinical and treatment-related variables in patients with moderate to severe activity of UC (partial Mayo score \geq 5) versus patients with mild or no activity (partial Mayo < 5).

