- Health resources (previous 3 years) will be described by IBD group and by disease activity, for the following events: drug therapies, number and type of imaging and laboratory testing, surgeries, number, reason and duration of hospitalizations, number and type of consultations with gastroenterologists or other medical specialists and adverse events.
- Health Care Resource Costs
Costs will be reported in total and on a per patient per month basis. Costs will be obtained by multiplying resource use with relevant unit costs. Unit costs for resource items will be collected by in Brazilian reliable administrative databases or other sources.

UC or CD-related health care costs. Consumer price index (CPI)-adjusted IBD-related health care costs will be computed as total costs, medical costs, drug costs, and other costs.

Treatment pattern costs. Treatment pattern costs will be calculated as total UC or CD-related health care costs, stratified by the defined treatment patterns.

In addition to the descriptive cost data, multivariate cost models may be developed where the observation time is divided into intervals of equal length.

For patients with active IBD at study appointment (Day 1), and included in the prospective period, the following analysis will be conducted:

- Descriptive statistics will be presented in a summary table, for the main socio-demographics, clinical characteristics and treatment regimen of the included patients at Day 1 (baseline), by IBD disease.
- The proportion of patients with active CD after 12 months among patients who had moderately to severely active CD at Day 1 (baseline) will be expressed as percentage and determined as

$$\frac{CD \text{ patients with } HBI \geq 8 \text{ or } CDAI > 220 \text{ after 12 months}}{Total \text{ CD patients with } HBI \geq 8 \text{ or } CDAI > 220 \text{ at Day 1}} \times 100$$

- Similarly, the proportion of patients with active UC after 12 months among those who had moderately to severely active UC at Day 1 (baseline) will be expressed as percentage and determined as:

$$\frac{UC \text{ patients with partial Mayo score } \geq 5 \text{ after 12 months}}{Total \text{ UC patients with partial Mayo score } \geq 5 \text{ at Day 1}} \times 100$$

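### Active Crohn's disease is CDAI ≥ 220 in the definitions but CDAI > 220 in the legible formulas for the primary and 12-month proportions: a minor inconsistency, but one inside the primary calculation

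*Protocol*

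**What the plan says.** **Definitions (≥ 220).** Protocol 10.1.1 sets the primary CD endpoint as the proportion with "active disease (HBI ≥ 8 or CDAI ≥ 220 points", judged on the criterion the site uses) at Day 1. Protocol 1.4 and SAP 5.1 say the same. Protocol 7.2 reads "Moderate to severe active CD is defined as" CDAI ≥ 220. The same cut-off appears in the objectives (Protocol 1.4 and 3, SAP 3.1), in the entry rule for the prospective period (Protocol 6.3.1, SAP 4.1) and in the active arm of the activity comparison (Protocol 1.4 and 10.1.1, SAP 5.2).

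**Formulas (> 220).** The primary formula in Protocol 10.2 and in SAP 7.5 counts CD patients with HBI ≥ 8 or CDAI > 220. The 12-month formula in Protocol 10.3 uses CDAI > 220 in the numerator and again, at Day 1, in the denominator. The SAP 7.6 counterpart is blacked out.

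**Comparison group.** Protocol 1.4 describes the other CD group as "mild or no activity (HBI < 8 or CDAI < 220 points"). Protocol 10.1.1 and SAP 5.2 give the same limits.

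**Which index.** The flow chart in Protocol 7.1 lists "Disease activity: CD (HBI score or CDAI"). Neither document says which index governs if a patient has both. SAP section 8, which lists clarifications to the protocol, does not mention the threshold.

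**The concern.** The two signs differ at one value, CDAI = 220, but that value is the decision limit of the primary CD endpoint. The formulas keep ≥ for HBI and for partial Mayo, so > is not simply how the authors write cut-offs; only the CDAI limb changes. The SAP disagrees with itself between 5.1 and 7.5.

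A programmer who follows the formula and one who follows the endpoint definition can each claim to have followed the plan and still report different numbers of active CD patients. The number active in the primary table could also differ from the number in the active group of the activity comparison, and from the number who entered follow-up on clinical score.

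**Working it through.** **1. The plan's own figures.** Protocol 10.6 gives about 400 patients, a CD/UC split of 50%/50% and a 20–30% rate of inadequate control.
- CD patients: 400 × 0.5 = 200.
- Active CD: 200 × 0.20 = 40 to 200 × 0.30 = 60. This reproduces the stated 40–60.
- Overall 95% margin at p = 0.5: 1.96 × √(0.25/400) = 4.9%, in line with the stated margin below 5%.

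Neither figure depends on the sign.

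**2. Classification under each rule.**

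| HBI | CDAI | Active by definition (≥ 220) | Active by formula (> 220) | No or mild as worded |
|---|---|---|---|---|
| – | 219 | no | no | yes |
| – | 220 | yes | no | no |
| – | 221 | yes | yes | no |
| 7 | – | no | no | yes |
| 8 | – | yes | yes | no |
| 7 | 220 | yes | no | yes |
| 9 | 180 | yes | yes | yes |
| 5 | 250 | yes | yes | yes |

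With one index per patient, the rules disagree only at CDAI = 220. That patient enters follow-up under Protocol 6.3.1 but is outside the denominator in Protocol 10.3. If the formula's active flag is carried into the activity comparison, the patient belongs to neither group. The last three rows need both indices in the same patient.

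**3. How many patients.** The documents give no CDAI distribution. As an illustration, assume that all 200 CD patients have whole-number CDAI scores, roughly normal with mean m and SD s. The share at exactly 220 is q = Φ((220.5 − m)/s) − Φ((219.5 − m)/s).

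| m | s | q | 200q | P(at least one) = 1 − (1 − q)^200 |
|---|---|---|---|---|
| 120 | 80 | 0.0023 | 0.46 | 0.37 |
| 120 | 100 | 0.0024 | 0.48 | 0.38 |
| 150 | 80 | 0.0034 | 0.68 | 0.49 |
| 150 | 100 | 0.0031 | 0.62 | 0.46 |
| 180 | 80 | 0.0044 | 0.88 | 0.59 |
| 180 | 100 | 0.0037 | 0.74 | 0.52 |

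So 0.5 to 0.9 patients are expected, and fewer in proportion as sites use HBI.

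**4. Effect on the Day 1 proportion.** Each such patient moves it by 1/200 = 0.5 point, always downward under >: 40/200 = 20.0% becomes 39/200 = 19.5%. The 95% margin for 200 CD patients is 1.96 × √(0.2 × 0.8/200) = 5.5 points at 20%, and 1.96 × √(0.3 × 0.7/200) = 6.4 points at 30%.

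**5. Effect on the 12-month proportion.** Let n be the CD patients active at Day 1 by the definition, and k those of them still active at month 12.
- Day 1 exactly 220, controlled at month 12: k/n becomes k/(n − 1), which is higher.
- Day 1 exactly 220, still active at month 12: k/n becomes (k − 1)/(n − 1), which is lower whenever k < n.
- Day 1 above 220, month 12 exactly 220: k/n becomes (k − 1)/n, lower by 1/60 = 1.7 to 1/40 = 2.5 points for n = 60 to 40.

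**The case against.** The strongest reply is that the effect is trivial. Under one patient is expected even if every CD patient has a CDAI, and that is an upper case. Protocol 7.2 says that CDAI draws on a 7-day diary and HBI needs none, and the study rules out extra monitoring, so many sites may record HBI only. Half a point against a margin of 5.5 to 6.4 points changes no conclusion of a mainly descriptive study. This stands, and it sets the severity.

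A second reply is that activity status may be settled elsewhere. The SAP contents list a derived-variables appendix that is not in the text available for this review, so how the flag is actually programmed cannot be established. This also stands. It does not remove the conflict between SAP 5.1 and SAP 7.5, and between Protocol 10.1.1 and Protocol 10.2.

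A reader might go further and infer that the word 'or' in the no-or-mild definition makes the two comparison groups overlap. The documents do not support that as a general finding. The primary endpoint is tied to the criterion each site uses, and the flow chart collects one index or the other. Read that way, the wording means below the cut-off on the site's index, which is a proper complement. Overlap needs a patient scored on both indices with discordant results. Nothing requires dual scoring, and no count of such patients is given. What remains is a small gap: the site qualifier is attached to the primary endpoint and not to the comparison groups, and no rule covers a patient who has both scores.

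**Conclusion.** The inconsistency is real and lies in the calculation of the primary CD endpoint. The definitions use CDAI ≥ 220, and the three legible formula locations (Protocol 10.2, Protocol 10.3, SAP 7.5) use CDAI > 220. It changes the status of a CDAI-only patient at one score. The expected number, below one, rests on the assumed distribution and on all 200 CD patients having a CDAI.

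Three stronger statements should not be made. The SAP 12-month formula cannot be counted as carrying the error, because it is blacked out. The bias is not one-directional throughout: the downward direction is assured for the Day 1 proportion only. Nothing shows that a sample size or a study conclusion would change. This is a minor consistency correction, worth making because two faithful readings of the plan can give different primary results.

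**What to change.** Replace CDAI > 220 with CDAI ≥ 220 in Protocol 10.2, in both parts of the Protocol 10.3 formula and in SAP 7.5, and in SAP 7.6 if it carries the same sign. This aligns the formulas with the stated endpoint and takes no view on the clinical merit of the cut-off.

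As a minor clarification, define no or mild activity as not meeting the active definition on the index that the site uses. The two groups are then exact complements even when a patient has both HBI and CDAI, and the site-criterion rule is preserved.

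The cost is a few words in the SAP, with a matching protocol correction or a line in SAP section 8, and one sign in the program. No new data are needed, and the planned sample size and margin do not change.
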